- AST or ALT $> 3 \times$ ULN and TBL $> 2 \times$ ULN (in subject with Gilbert's syndrome: AST or ALT $> 3 \times$ ULN and direct bilirubin $> 1.5 \times$ ULN)
- TBL $> 3 \times$ ULN
- Grade ≥ 3 nonhematological AE except for Grade 3 rash that has improved to Grade 0 or 1 or Grade ≥ 3 endocrinopathies that are managed to Grade 0 or 1 with replacement therapy.
- Persistent Grade ≥ 2 AEs requiring ASP1948 interruption that do not recover to Grade 0 or 1 within 12 weeks after the last dose with steroid treatment tapered to physiological replacement doses (≤ 10 mg prednisone or equivalent) of study treatment. However, subjects with a persistent Grade ≥ 2 AE requiring ASP1948 interruption may continue on study treatment if asymptomatic and controlled, with investigator and sponsor agreement
- Grade ≥ 2 pneumonitis
- Guillain-Barré syndrome or myasthenic syndrome/myasthenia gravis
- Grade ≥ 2 encephalopathy, meningitis or Grade ≥ 2 motor or sensory neuropathy
- Any toxicity that results in the inability to reduce corticosteroid dose to 10 mg or less of prednisone or equivalent per day within 12 weeks
- Grade 3 or 4 IRRs

Toxicities Requiring ASP1948 Treatment Interruption

ASP1948 treatment will be withheld for the following toxicities if there is a reasonable possibility that the event may have been caused by ASP1948:

- Grade 4 neutropenia or Grade ≥ 3 febrile neutropenia
- Grade 4 thrombocytopenia or Grade 3 thrombocytopenia accompanied by bleeding that requires any transfusion
- Grade 4 anemia or Grade 3 anemia requiring transfusion
- Grade 3 rash or Grade 3 endocrinopathies
- AST or ALT ≥ 3.0 and $\leq 5.0 \times$ ULN or TBL > 1.5 and $\leq 3 \times$ ULN (in subject with Gilbert's syndrome: AST or ALT ≥ 3.0 and $\leq 5.0 \times$ ULN or direct bilirubin $> 1.5 \times$ ULN) in subjects without liver metastases
- AST or ALT ≥ 3.0 and $\leq 8.0 \times$ ULN or TBL > 1.5 and $\leq 3 \times$ ULN (in subjects with Gilbert's syndrome: AST or ALT ≥ 5.0 and $\leq 8.0 \times$ ULN or direct bilirubin $> 1.5 \times$ ULN) in subjects with liver metastases
- Any Grade 2 or higher irAE (including but not limited to those listed below):
 - colitis or diarrhea
 - hypophysitis
 - adrenal insufficiency
 - nephritis
 - ocular inflammatory toxicity

- pancreatitis
- new-onset neurological symptoms or signs (other than Grade 2 or higher encephalopathy, meningitis or Grade 2 or higher motor or sensory neuropathy, which require permanent discontinuation of ASP1948 treatment)
- IRR

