
Additionally, ASP1948 treatment may be interrupted for any AE, laboratory abnormality or intercurrent illness that in the judgment of the investigator warrants delaying dosing of ASP1948 treatment.

Criteria for Resuming Study Treatment

Dosing may be delayed for up to 12 weeks from the end of the prior treatment cycle for recovery of toxicity requiring IP treatment interruption. IP treatment may be resumed if the AEs have recovered to Grade 0 or 1 and steroid treatment tapered to physiological replacement doses (≤ 10 mg per day prednisone or equivalent) and do not meet the criteria for permanent discontinuation of study treatment. Interruption for COVID-19-related illness is limited to 12 weeks. Study treatment may be resumed in the absence of COVID-19-related symptoms per investigator judgement.

Concomitant Treatment (Medication and Nonmedication Therapy) Restrictions or Requirements:

- *Investigational agents:* The use of investigational agents is not allowed during study treatment.
- *Steroids and other immunosuppressive therapy:* The use of immunosuppressive agents and immunosuppressive doses of systemic steroids (> 30 mg/day of hydrocortisone, > 10 mg/day of prednisone, > 2 mg/day of dexamethasone or equivalent) is not allowed during study treatment unless needed to manage AEs related to study treatment. The use of topical, ocular, intra-articular, intranasal and inhalational corticosteroids (with minimal systemic absorption) is allowed. Physiologic replacement doses of systemic corticosteroids (≤ 30 mg/day of hydrocortisone or ≤ 10 mg/day of prednisone or equivalent) are permitted. Corticosteroids for prophylaxis (e.g., contrast dye allergy) or for brief treatment of conditions not related to study treatment (e.g., delayed-type hypersensitivity reaction caused by a contact allergen) is also allowed.
- *Vaccines:* Live vaccines are prohibited while the subject is receiving study treatment and for 14 days after last dose of study treatment. Examples of live vaccines include, but are not limited to, the following: measles, mumps, rubella, chicken pox, yellow fever, Bacillus Calmette-Guerin (BCG) and typhoid vaccine.

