2.1.1.2.2 Phase 1 Results (1948-CL-0102)

As of data cut-off of Apr 26, 2021, safety data from 9 patients with advanced solid tumors exposed to ASP1948 are available. Patients received ASP1948 monotherapy at 1200 mg (n = 3) or 2000 mg (n = 3) Q2W or 3000 mg (n = 3) Q3W.

Preliminary pharmacokinetic data from Study 1948-CL-0102 monotherapy escalation cohorts revealed that ASP1948 C_{max} and AUC_{14-day} increased dose dependently after the first dose.

Preliminary response data in Study 1948-CL-0102 (data cutoff 26 Apr 2021) for the 9 patients treated with ASP1948 monotherapy showed that 1 (11.1%) patient had confirmed PR at the 1200-mg dose level, 2 (22.2%) patients had stable disease and 6 (66.7%) patients had PD as their BOR using RECIST 1.1. No patients had a confirmed CR using RECIST 1.1 or iRECIST.

8 (88.9%) of 9 patients dosed with ASP1948 monotherapy experienced TEAEs, 7 (77.8%) patients experienced at least 1 TEAE considered to be related to ASP1948 by the investigator and 2 (22.2%) patients experienced TEAEs that were CTCAE grade ≥ 3 . Two (22.2%) patients experienced a total of 2 serious TEAEs. One (11.1%) patient experienced a TEAE that led to death (malignant neoplasm progression) which was considered not related to ASP1948 by the investigator. There were no irAEs. IRRs were experienced by 1 (11.1%) patient at the 3000-mg dose level. There were no dose-limiting toxicities up to the 3000-mg dose level.

Refer to the current IB for additional details.

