4.1.4 Dose Limiting Toxicity Criteria

A DLT is defined as any of the following AEs (graded using National Cancer Institute Common Terminology Criteria for Adverse Events [NCI-CTCAE] Version 4.03) that the investigator (or sponsor) cannot clearly attribute to a cause other than IP:

- Grade 4 neutropenia or Grade \geq 3 febrile neutropenia
- Grade 4 thrombocytopenia or Grade 3 thrombocytopenia accompanied by bleeding that requires any transfusion
- Grade 4 anemia or Grade 3 anemia requiring transfusion
- Grade \geq 3 nonhematological AE (excluding asymptomatic changes to amylase, lipase and hypophosphatemia)
- Grade \geq 2 pneumonitis

- Aspartate aminotransferase (AST) or alanine aminotransferase (ALT) > 5 × upper limit of normal (ULN; Grade ≥ 3) in subjects without liver metastases
- AST or ALT > 8 × ULN in subjects with liver metastases
- AST or ALT > 3 × ULN and total bilirubin (TBL) > 2 × ULN (in subject with Gilbert's syndrome: AST or ALT > 3 x ULN and direct bilirubin > 1.5 x ULN)
- TBL > 3 × ULN (Grade ≥ 3)
- Grade ≥ 2 encephalopathy, meningitis or Grade ≥ 2 motor or sensory neuropathy
- Grade ≥ 2 pulmonary or central nervous system (CNS) hemorrhage
- Grade ≥ 3 hemorrhage
- Any grade arterial thrombotic event (angina, myocardial infarction, transient ischemic attack [TIA], cerebrovascular accident [CVA] and any other arterial thromboembolic event)
- Any grade gastrointestinal perforation
- Any grade wound dehiscence
- Guillain-Barré syndrome or myasthenic syndrome/myasthenia gravis
- IRR that requires the infusion to be discontinued

Febrile neutropenia, thrombocytopenia accompanied by bleeding that requires any transfusion, and anemia requiring transfusion regardless of grade, may be considered DLTs by the investigator (or sponsor). In addition, in case the second and/or third dose for Dose level A and Dose level B, or the second dose for Dose level C cannot be performed within 7 days after a scheduled visit for drug related toxicities not specified in the above bullet list, this may be also considered DLTs by the investigator (or sponsor).

Subjects who are tolerating IP at a dose level that is being reviewed due to the occurrence of DLTs in another subject will not be automatically precluded from continued dosing during the safety review, and will be allowed to continue dosing for as long as tolerated unless directed otherwise as a result of the safety review by the DESC.

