6.7.1 Toxicities Requiring Permanent Discontinuation of ASP1948 Treatment

ASP1948 treatment will be permanently discontinued for the following toxicities that are assessed as related to ASP1948, if there is a reasonable possibility that the event may have been caused by ASP1948:

- Hematological toxicity requiring ASP1948 treatment interruption that does not recover to Grade 0 or 1 within 4 weeks
- AST or ALT $> 5 \times$ ULN (Grade ≥ 3) in subjects without liver metastases
- AST or ALT $> 8 \times$ ULN in subjects with liver metastases
- AST or ALT $> 3 \times$ ULN and TBL $> 2 \times$ ULN (in subject with Gilbert's syndrome: AST or ALT $> 3 \times$ ULN and direct bilirubin $> 1.5 \times$ ULN)
- TBL $> 3 \times$ ULN
- Grade ≥ 3 nonhematological AE except for Grade 3 rash that has improved to Grade 0 or 1 or Grade ≥ 3 endocrinopathies that are managed to Grade 0 or 1 with replacement therapy.
- Persistent Grade ≥ 2 AEs requiring ASP1948 interruption that do not recover to Grade 0 or 1 within 12 weeks after the last dose with steroid treatment tapered to physiological replacement doses (≤ 10 mg prednisone or equivalent) of study treatment. However, subjects with a persistent Grade ≥ 2 AE requiring ASP1948 interruption may continue on study treatment if asymptomatic and controlled, with investigator and sponsor agreement
- Grade ≥ 2 pneumonitis
- Guillain-Barré syndrome or myasthenic syndrome/myasthenia gravis
- Grade ≥ 2 encephalopathy, meningitis or Grade ≥ 2 motor or sensory neuropathy
- Any toxicity that results in the inability to reduce corticosteroid dose to 10 mg or less of prednisone or equivalent per day within 12 weeks
- Grade 3 or 4 IRRs

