12.5 Liver Safety Monitoring and Assessment

The purpose of this appendix is to provide guidance for the monitoring of DILI during the course of the study. It should be noted that this section does not specify the end of study analyses of liver enzymes. The end of study liver enzymes analyses will be described in the SAP. Any subject enrolled in a study with active drug therapy and who reveals an increase of serum aminotransferases (AT) to $> 3 \times \text{ULN}$ (to $> 5 \times \text{ULN}$ in subjects with liver metastases) or TBL $> 2 \times \text{ULN}$ should undergo detailed testing for liver enzymes (including at least alkaline phosphatase [ALP], ALT, AST and TBL). Testing should be repeated within 72 hours of notification of the test results. For studies for which a central laboratory is used, alerts will be generated by the central laboratory regarding moderate and severe liver abnormality to inform the investigator and study team. Subjects should be asked if they have any symptoms suggestive of hepatobiliary dysfunction.

Definition of Liver Abnormalities

Confirmed abnormalities will be characterized as moderate and severe where ULN is as shown in [Table 12](#).

Table 12 Moderate and Severe Liver Abnormalities

	ALT or AST		Total Bilirubin
Moderate	$> 3 \times \text{ULN}$ (in patients without liver metastases), $> 5 \times \text{ULN}$ (in patients with liver metastases)	or	$> 2 \times \text{ULN}$
Severe	$> 3 \times \text{ULN}$	and†	$> 2 \times \text{ULN}$

ALT: alanine aminotransferase; AST: aspartate aminotransferase; ULN: upper limit of normal

†Samples taken simultaneously or within a maximum of 24 hours.

In addition, the subject should be considered to have severe hepatic abnormalities for any of the following:

- ALT or AST $> 8 \times \text{ULN}$
- ALT or AST $> 5 \times \text{ULN}$ for more than 2 weeks (in the absence of liver metastases)
- ALT or AST $> 3 \times \text{ULN}$ and† TBL $> 2 \times \text{ULN}$ or INR > 1.5 (If INR testing is applicable/evaluated)
- ALT or AST $> 3 \times \text{ULN}$ with the appearance of fatigue, nausea, vomiting, right upper quadrant pain or tenderness, fever, rash and/or eosinophilia ($> 5\%$)

The investigator may determine that abnormal liver function results, other than those described above, may qualify as moderate or severe abnormalities and require additional monitoring and follow-up.

Follow-up Procedures

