Study Treatment Discontinuation

In the absence of an explanation for increased LFTs, such as viral hepatitis, preexisting or acute liver disease, presence of liver metastases, or exposure to other agents associated with liver injury, the subject may be discontinued from study treatment. The investigator may determine that it is not in the subject’s best interest to continue study treatment.

Discontinuation of study treatment should be considered if:

- AST or ALT $> 8 \times$ ULN
- AST or ALT $> 5 \times$ ULN for more than 2 weeks
- ALT or AST $> 3 \times$ ULN and† TBL $> 2 \times$ ULN or INR > 1.5) (if INR testing is applicable/evaluated)
- ALT or AST $> 3 \times$ ULN with the appearance of fatigue, nausea, vomiting, right upper quadrant pain or tenderness, fever, rash and/or eosinophilia ($> 5\%$)

† Samples taken simultaneously or within a maximum of 24 hours.

In addition, if close monitoring for a subject with moderate or severe hepatic laboratory tests is not possible, study treatment should be discontinued.

Hy's Law Definition:

1. Evidence that a drug can cause hepatocellular-type injury, generally shown by a higher rate than control of people with $3 \times$ AT elevations over the ULN ($2 \times$ elevations are too common in treated and untreated patients to be discriminating).
2. Cases of increased bilirubin (to at least $2 \times$ ULN) in people with concomitant AT elevation to at least $3 \times$ ULN (but it is almost invariably higher) and no evidence of intra- or extra-hepatic bilirubin obstruction (elevated ALP) or Gilbert's syndrome [Temple, 2006].

FDA Guidance for Industry titled "Drug-induced Liver Injury: Premarketing Clinical Evaluation" issued by the FDA on July 2009:

FDA Guidance for Industry:

1. The drug causes hepatocellular injury, generally shown by a higher incidence of 3-fold or greater elevations above the ULN of ALT or AST than the (nonhepatotoxic) control drug or placebo.
2. Among subjects showing such AT elevations, often with AT levels much greater than $3 \times$ ULN, 1 or more also show elevation of serum TBL to $> 2 \times$ ULN, without initial findings of cholestasis (elevated serum ALP).
3. No other reason can be found to explain the combination of increased AT and TBL, such as viral Hepatitis A, B or C; preexisting or acute liver disease; or another drug capable of causing the observed injury.

Reference

Temple R. Hy's Law: Predicting Serious Hepatotoxicity. *Pharmacoepidemiol Drug Saf.* 2006; 15(4):241-3.

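### With liver metastases, the mandatory AST/ALT hold starts at 3.0 x ULN without Gilbert's syndrome but at 5.0 x ULN with it, and no reason is given

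*Protocol*

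**What the plan says.** The synopsis (Toxicities Requiring ASP1948 Treatment Interruption) and Section 6.7.2 list toxicities for which treatment must be withheld if ASP1948 may reasonably have caused them. Two bullets concern liver tests.

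- **No liver metastases:** hold at AST or ALT 3.0 to 5.0 x ULN. The Gilbert's parenthesis keeps the same lower limit: "in subject with Gilbert's syndrome: AST or ALT ≥ 3.0 and" up to 5.0 x ULN.
- **Liver metastases:** hold at AST or ALT 3.0 to 8.0 x ULN. The Gilbert's parenthesis reads "in subjects with Gilbert's syndrome: AST or ALT ≥ 5.0 and" up to 8.0 x ULN.

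The synopsis and Section 6.7.2 give identical AST/ALT figures, so the difference is not confined to the summary. Each parenthesis also replaces the total bilirubin limb with a direct bilirubin limb. This point concerns the transaminase figure only.

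**The concern.** Everywhere else in the Protocol, Gilbert's syndrome changes only the bilirubin measure. Here it also moves the transaminase limit, from 3.0 to 5.0 x ULN, without explanation, and only for subjects who also have liver metastases.

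At stake is a safety instruction that sites will follow literally. A subject with both conditions and a possibly drug-related AST/ALT of, say, 4 x ULN would not have to be held on that value, although every other subject with the same value would. The liver is a relevant organ for this drug. Section 2.1.1.2.1 reports three dose-limiting events in two patients at 2000 mg in Study 1948-CL-0101. Hepatic enzyme increase and hepatic failure were two of the three, and hepatic failure is also listed among the fatal events considered related to ASP1948.

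**Working it through.** There is no sample size or error rate to reproduce. The check sets the thresholds side by side and then sizes the affected subgroup.

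**1. Lower AST/ALT limit for a mandatory hold (synopsis and Section 6.7.2)**

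| Liver metastases | Gilbert's | Lower limit (x ULN) | Upper limit (x ULN) |
|---|---|---|---|
| No | No | 3.0 | 5.0 |
| No | Yes | 3.0 | 5.0 |
| Yes | No | 3.0 | 8.0 |
| Yes | Yes | 5.0 | 8.0 |

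Three of the four combinations hold from 3.0 x ULN. The Gilbert's difference is 3.0 − 3.0 = 0 without metastases and 5.0 − 3.0 = 2.0 x ULN with them. Above the upper limits, the permanent discontinuation rules take over.

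**2. How other rules treat Gilbert's syndrome**

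- Section 4.1.4, combined DLT rule: AST/ALT > 3 x ULN with or without Gilbert's; only the bilirubin part changes ("in subject with Gilbert's syndrome: AST or ALT > 3 x ULN and direct bilirubin > 1.5 x ULN").
- Section 6.7.1, combined discontinuation rule: the same structure, with AST/ALT > 3 x ULN either way.
- Section 5.1, inclusion criterion 8: the Gilbert's exception is in the bilirubin row only; AST/ALT must be ≤ 2.5 x ULN for everyone.
- Appendix 12.5, Table 12: the moderate-abnormality limit is > 3 x ULN without and > 5 x ULN with liver metastases, with no Gilbert's distinction.

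The liver-metastases hold bullet is therefore the only place where Gilbert's status moves a transaminase limit.

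**3. Can another reading remove the difference?**

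- If the parenthesis is read as adding to the main rule, the range 3.0 to 8.0 already contains 5.0 to 8.0, so the 5.0 would have no effect.
- A higher baseline does not explain it. All subjects enter at ≤ 2.5 x ULN, so 3.0 to below 5.0 x ULN is above the entry limit in either group.

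**4. Which figure is the slip?** The bullet for subjects without metastases points to 3.0 in the parenthesis. Appendix 12.5 points to 5.0 for everyone with liver metastases, which would make the general 3.0 the error. The text does not settle it.

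**5. Expected subgroup size.** The Protocol gives no frequency for subjects with both conditions. Assume a proportion p of 1% to 5%; expected number = N x p.

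| N (source) | p = 1% | p = 5% |
|---|---|---|
| 9 treated by the data cut-off (Section 2.1.1.2.2) | 9 x 0.01 = 0.09 | 9 x 0.05 = 0.45 |
| 18 planned (Section 9.1) | 18 x 0.01 = 0.18 | 18 x 0.05 = 0.90 |
| 27 maximum evaluable (Section 9.1) | 27 x 0.01 = 0.27 | 27 x 0.05 = 1.35 |

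These counts come before requiring any enzyme rise.

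**The case against.** The synopsis and Section 6.7.2 agree with each other, and the Protocol gives no reason for any of its hold thresholds, so a missing reason does not by itself show an error. The combined DLT and discontinuation rules pair transaminases with bilirubin and ignore metastases as well as Gilbert's, so they say little about an isolated rise in a subject with liver metastases. That leaves one like-for-like comparator, the bullet for subjects without metastases. Appendix 12.5 actually supports 5.0 for liver metastases.

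Other protections also narrow the gap:

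- Grade 2 or higher immune-related events require a hold, and Appendix 12.9 names hepatitis as a potential one.
- The direct bilirubin limb of the same bullet triggers a hold on its own.
- AST/ALT > 3 x ULN with direct bilirubin > 1.5 x ULN leads to permanent discontinuation.
- Appendix 12.5 asks sites to consider stopping treatment at > 3 x ULN with INR > 1.5 or "with the appearance of fatigue, nausea, vomiting, right upper quadrant pain or tenderness, fever, rash and/or eosinophilia".
- Investigators have discretion: "ASP1948 treatment may be interrupted for any AE, laboratory abnormality or intercurrent illness that in the judgment of the investigator" warrants a delay.
- Serum chemistry is scheduled on Day 1 of every cycle, so a rise would be seen.

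Finally, at the data cut-off all three dose levels had been opened, with 3 subjects each and no DLTs, so the rows for 18 and 27 subjects are planning figures.

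Most of this stands, and it limits the weight of the point. It does not remove it. Discretion is optional, the Appendix 12.5 stopping provisions are to be considered rather than applied, and the immune-related hold needs a judgement that the event is immune-related. An isolated, asymptomatic rise not judged immune-related still has no mandatory hold in this one subgroup.

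**Conclusion.** The concern holds. The two lower limits in the liver-metastases bullet differ by 2.0 x ULN according to Gilbert's status, without a stated reason and against the pattern of every other liver rule in the Protocol. That the limits differ is certain; which figure is wrong is not. If 3.0 was intended throughout, subjects with both conditions lose a mandatory hold between 3.0 and below 5.0 x ULN. If 5.0 was intended for liver metastases, subjects with metastases but without Gilbert's are held earlier than planned.

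The reach is small: fewer than one subject with both conditions is expected among the planned 18, on the assumed 1% to 5%. The DLT criteria, the BOIN decision table, the analysis sets and the endpoints are unaffected. It is a minor correction, but it should be made because the threshold directly governs dosing.

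**What to change.** In the synopsis and in Section 6.7.2, give the liver-metastases hold bullet one lower AST/ALT limit, whatever the Gilbert's status.

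- **Default:** change 5.0 to 3.0 x ULN in the Gilbert's parenthesis. This is the more protective value and already applies to all other subjects. The cost is one number in two places and perhaps an occasional extra hold in a very small subgroup.
- **Alternative:** if the medical lead confirms that 5.0 x ULN was meant for liver metastases, in line with Appendix 12.5, use 5.0 for all such subjects. This gives up the mandatory hold at 3.0 to below 5.0 x ULN for everyone with liver metastases, so it should be a deliberate clinical decision rather than an editorial one.

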1.2 Study Schema

Figure 1 Study Schema

DLT: dose limiting toxicity

- The DLT observation period will be 28 days for Dose level A and Dose level B, or 21 days for Dose level C.
- Dose level B would only be opened if Dose level A is deemed tolerable.
- Dose level C would only be opened if Dose level B is deemed tolerable.
- Subjects assigned to Dose level A (ASP1948, 1200 mg) are allowed to dose escalate to 2000 mg (if it is deemed tolerable) at the discretion of the investigator provided the subject did not experience a DLT.
- End of Treatment visit will occur within 7 days of last dose or decision by the investigators to discontinue the subject from study treatment.

1.3 Schedule of Assessments

Table 1 Schedule of Assessments for Dose level A and Dose level B

Assessments	Screening	Treatment Period								Follow-up	
		Cycle 1				Cycle 2 ^a		Cycles 3~	End of Treatment	Safety Follow-up	
Cycle Day	-28 to -1	1	2	3	8	1	8	1			30 days from last dose
Visit Window (Days) ^c	0	0	0	0	0	+ 1	+ 1	± 3 ^s	+ 7	+ 3	± 7
General Study Procedures											
Informed Consent	X										
Verify Inclusion/Exclusion	X	X									
Medical History/Disease History/Demographics	X										
Height	X										
Weight	X	X				X		X	X		
Vital Signs	X	X ^d			X	X ^d	X	X ^d	X	X	X
Physical Examination (including auscultation) ^e	X	X			X	X		X	X		
ECOG Performance Status	X	X				X		X	X	X	
Prior/Concomitant Medications ^f		Every visit									
AE Assessment ^g		Every visit									X
Blood Collection											
Hepatitis B and C Testing ^h	X										
Hepatitis B Virus antibody (if HBsAg positive) ^h	X										
HCV RNA (if HCV positive) ^h	X										
CBC with Differential ⁱ	X	X				X		X	X	X	
Serum Chemistries ⁱ	X	X				X		X	X	X	
Coagulation ⁱ	X	X				X		X	X	X	
TSH and Free T4 ⁱ	X					X		X ^j		X	

Assessments	Screening	Treatment Period								Follow-up	
		Cycle 1				Cycle 2 ^a		Cycles 3~	End of Treatment	Safety Follow-up	
Cycle Day	-28 to -1	1	2	3	8	1	8	1		30 days from last dose	90 days from last dose ^b
Visit Window (Days) ^c	0	0	0	0	0	+1	+1	±3 ^s	+7	+3	±7
Pregnancy Test ^{i,k}	X	X				X		X	X		
Testosterone (mCRPC only)	X										
PSA (mCRPC only) ^l	X	Every 8 weeks (± 1 week) from C1D1 until iCPD									
Tumor Marker ^m		Per standard of care or as clinically indicated									
Whole blood - Immune Cell Subsets (flow cytometry) ⁿ		X			X	X		X	X		
Serum for Circulating Soluble Factors and Cytokines/Chemokines and Oncomarker		See [Table 3] for Sample Collection Schedule									
Serum for Pharmacokinetics		See [Table 3] for Sample Collection Schedule									
Receptor Occupancy		See [Table 3] for Sample Collection Schedule									
Antidrug Antibodies (immunogenicity)		See [Table 3] for Sample Collection Schedule									
Optional Whole Blood Sample (banked for Pharmacogenomics analysis)		X									
Urine Collection											
Urinalysis ^l	X	X				X		X	X		
Tumor Tissue Collection											
Optional Archival Tumor Sample ^o	X										
Radiographic Imaging											
Tumor Imaging ^p	X	Every 8 weeks (± 1 week) from C1D1 until iCPD									
Electrocardiograms											
12-lead ECG ^q	X	See [Table 3] for ECG Schedule									
Study Drug Administration											
ASP1948 (60-minute Infusion -5 to +20 minutes) ^r		X				X		X			

C: cycle; C1D1: Cycle 1 Day 1; CBC: complete blood count; CT: computed tomography; d: day; DLT: dose limiting toxicity; ECG: electrocardiogram; ECOG: Eastern Cooperative Oncology Group; eCRFs: electronic case report forms; FFPE: formalin-fixed, paraffin-embedded; HBsAg: Hepatitis B surface antigen; HBV: Hepatitis B virus; HCV: Hepatitis C

virus; iCPD: immune confirmed progressive disease by iRECIST; IP: investigational product; mCRPC: metastatic castration resistant prostate cancer; MRI: magnetic resonance imaging; PSA: prostate specific antigen; T4: thyroxine; TSH: thyroid stimulating hormone

Footnotes on next page

- a. For C2D8, if in the investigator's opinion the subject is clinically stable, a telephone contact to the subject to assess adverse events and concomitant medication use can be performed in lieu of an onsite visit. In these instances, the subject will not be required to perform vital signs.
- b. The 90-day safety follow-up visit is optional for subjects who discontinue due to progressive disease or initiate new anticancer treatment after the last dose of IP.
- c. The visit window for Day 1 of each cycle is calculated from the actual Day 1 of last cycle. The visit window for Day 8 of each cycle is calculated from the actual Day 1 of the cycle. End of Treatment visit will occur within 7 days of last dose or decision by the investigators to discontinue the subject from treatment.
- d. Obtain vital signs within 15 minutes prior to start of ASP1948 dosing, every 15 minutes (-5 to + 10 minutes window) during ASP1948 dosing, at the end of ASP1948 dosing (-5 to + 10 minutes window) and 30 minutes (\pm 10 minutes) after completion of ASP1948 dosing.
- e. As a result of auscultation, a chest X-ray examination, sialylated carbohydrate antigen (KL-6) and transcutaneous arterial oxygen saturation (SpO₂) may be performed if clinically indicated.
- f. Includes any prior antitumor medications related to the primary cancer and all anticancer treatment that is taken within 28 days prior to IP administration.
- g. AEs will be collected from the time of informed consent through 30 days following the last dose of IP or until initiation of a new anticancer treatment or the subject is determined to be a screen failure, whichever comes first. SAEs (regardless of causality) will be collected from the time of informed consent through 90 days following the last dose of IP or until initiation of a new anticancer treatment or the subject is determined to be a screen failure, whichever comes first.
- h. HBsAg, Immunoglobulin M antibody to Hepatitis B core antigen (IgM anti-HBc), total antibody to Hepatitis B core antigen (total anti-HBc) (confirmed by HBV DNA using the polymerase chain reaction) will be assessed during HBV testing. HBc antibodies will be tested, if HBsAg is positive. HCV antibody will be tested and HCV RNA will be detected, if HCV antibody is positive.
- i. Screening safety laboratory tests should be done within 7 days prior to the initiation of IP. After Cycle 1, safety laboratory tests on Day 1 of each cycle can be performed up to 72 hours prior to scheduled treatment point.
- j. TSH and free T4 to be measured on Day 1 of every other cycle after Cycle 2 (i.e., C4, C6, C8, etc.) and at the 30-day safety follow-up visit.
- k. Urine or serum pregnancy test will be performed in women of childbearing potential. Testing at treatment visits must occur prior to IP administration.
- l. PSA (mCRPC only) will be collected within 14 days prior to C1D1 and while on study approximately every 8 weeks (i.e., C5, C9, C13, etc.).
- m. Information regarding tumor marker (e.g., CA-125) tests done as a standard of care may be recorded in the eCRFs, if available.
- n. Samples should be collected predose at C1D1, C2D1, C3D1, C5D1. Samples are also collected on C1D8 and at the End of Treatment visit.
- o. Archival tumor specimen is optional. A minimum of 1 FFPE tumor tissue block with adequate viable tumor cells (preferred) OR a minimum of 10 FFPE unstained serial slides are required. If \geq 10 slides cannot be provided, the sponsor should be contacted for further guidance.
- p. To ensure comparability, the same technique (CT/MRI) used at Screening should be utilized throughout the study. Imaging should include chest, abdomen and pelvis, as well as any other anatomical region appropriate for the subject's disease. Scans performed prior to informed consent as standard of care are acceptable as screening scans, if done within 28 days prior to C1D1.
- q. Prior to performing ECG, subjects should rest in supine position (or semirecumbent, if supine is not tolerated) for 10 minutes. When ECGs are performed in triplicates, it should be recorded with 2 minutes apart per time point. Single ECG will be done at Screening and End of Treatment. All ECGs will be submitted for central read.
- r. ASP1948 is administered on Day 1 of each 14-day cycle. In principle, subjects must be hospitalized from C1D1 (first dose of ASP1948) to C2D14. If it is deemed possible to follow a subject on an outpatient basis based on his/her physical condition, etc. during the DLT observation period, the investigator must ensure his/her safety under outpatient management by performing the tests considered clinically necessary before discharge (observation and evaluation of general condition, blood tests, etc.). For the next 3 doses (third, fourth and fifth infusions), subjects should remain at the site facility for at least 2 hours after completion of ASP1948 administration. The subject should be instructed to notify site personnel if the subject develops any AEs during this time period.
- s. The visit window of Cycle 3 Day 1 is "+3".

Table 2 Schedule of Assessments for Dose level C

Assessments	Screening	Treatment Period										Follow-up		
		Cycle 1					Cycle 2			Cycles 3 -		End of Treatment	Safety Follow-up	
Cycle Day	-28 to -1	1	2	3	8	15	1	8 ^a	15	1	15 ^a			30 days from last dose
Visit Window (Days) ^c		0	0	0	0	0	+2	±2	±2	±2	±2	+7	+3	±7
General Study Procedures														
Informed Consent	X													
Verify Inclusion/Exclusion	X	X												
Medical History/Disease History/Demographics	X													
Height	X													
Weight	X	X					X			X		X		
Vital Signs	X	X ^d			X	X	X ^d	X	X	X ^d	X	X	X	X
Physical Examination (including auscultation) ^e	X	X				X	X			X		X		
ECOG Performance Status	X	X					X			X		X	X	
Prior/Concomitant Medications ^f		Every visit												
AE Assessment ^g		Every visit											X	
Blood Collection														
Hepatitis B and C Testing ^h	X													
Hepatitis B virus antibody (if HBsAg positive) ^h	X													
HCV RNA (if HCV positive) ^h	X													
CBC with Differential ⁱ	X	X				X	X		X	X		X	X	
Serum Chemistries ⁱ	X	X				X	X		X	X		X	X	
Coagulation ⁱ	X	X				X	X		X	X		X	X	
TSH and Free T4 ⁱ	X						X			X ^j			X	
Pregnancy Test ^{i,k}	X	X					X			X		X		
Testosterone (mCRPC only)	X													
PSA (mCRPC only) ^l	X	Every 9 weeks (± 1 week) from C1D1 until iCPD												

Assessments	Screening	Treatment Period										Follow-up		
		Cycle 1					Cycle 2			Cycles 3 -		End of Treatment	Safety Follow-up	
Cycle Day	-28 to -1	1	2	3	8	15	1	8 ^a	15	1	15 ^a		30 days from last dose	90 days from last dose ^b
Visit Window (Days) ^c		0	0	0	0	0	+2	± 2	± 2	± 2	± 2	+7	+3	± 7
Tumor Marker ^m	Per standard of care or as clinically indicated													
Whole blood - Immune Cell Subsets (flow cytometry) ⁿ		X			X		X			X		X		
Serum for Circulating Soluble Factors and Cytokines/Chemokines and Oncomarker	See [Table 4] below for Sample Collection Schedule													
Serum for Pharmacokinetics	See [Table 4] below for Sample Collection Schedule													
Receptor Occupancy	See [Table 4] below for Sample Collection Schedule													
Anti-drug Antibodies (Immunogenicity)	See [Table 4] below for Sample Collection Schedule													
Optional whole blood sample (banked for Pharmacogenomics analysis)		X												
Urine Collection														
Urinalysis ⁱ	X	X				X	X		X	X		X		
Tumor Tissue Collection														
Optional Tumor Samples ^o	X								X					
Radiographic Imaging														
Tumor Imaging ^p	X	Every 9 weeks (± 1 week) from C1D1 until iCPD												
Electrocardiograms														
12-lead ECG ^q	X	See [Table 4] below for ECG schedule												
Study Treatment Administration														
ASP1948 (60 minute Infusion -5 to +20 minutes) ^r		X					X			X				

C: cycle; C1D1: Cycle 1 Day 1; CBC: complete blood count; CT: computed tomography; d: day; DLT: dose limiting toxicity; ECG: electrocardiogram; ECOG: Eastern Cooperative Oncology Group; eCRFs: electronic case report forms; FFPE: formalin fixed, paraffin embedded; HBsAg: Hepatitis B surface antigen; HBV: Hepatitis B virus; HCV: Hepatitis C virus; iCPD: immune confirmed progressive disease by iRECIST; IP: investigational product; mCRPC: metastatic castration resistant prostate cancer; MRI: magnetic resonance imaging; PSA: prostate specific antigen; T4: thyroxine; TSH: thyroid stimulating hormone

- a. For visits where the only procedures required are vital sign assessment, adverse event review and concomitant medication review, if in the investigator's opinion the subject is clinically stable, a telephone contact to the subject to assess adverse events and concomitant medication use can be performed in lieu of an onsite visit. In these instances, assessment of the subject's vital signs will not be required.
- b. The 90-day safety follow-up visit is optional for subjects who discontinue due to progressive disease or initiate new anticancer treatment after the last dose of IP.
- c. The visit window for Day 1 of each cycle is calculated from the actual Day 1 of last cycle. The visit window for Day 8 and 15 of each cycle is calculated from the actual Day1 of the cycle. End of Treatment visit will occur within 7 days of last dose or decision by the investigators to discontinue the subject from treatment.
- d. Obtain vital signs within 15 minutes prior to start of ASP1948 dosing, every 15 minutes (-5 to + 10 minutes window) during ASP1948 dosing, at the end of ASP1948 dosing (-5 to + 10 minutes window) and 30 minutes (\pm 10 minutes) after completion of ASP1948 dosing.
- e. As a result of auscultation, a chest X-ray examination, sialylated carbohydrate antigen (KL-6) and transcutaneous arterial oxygen saturation (SpO₂) may be performed if clinically indicated.
- f. Includes any prior antitumor medications related to the primary cancer and all anticancer treatment that is taken within 28 days prior to IP administration.
- g. AEs will be collected from the time of informed consent through 30 days following the last dose of IP or until initiation of a new anticancer treatment or the subject is determined to be a screen failure, whichever comes first. SAEs (regardless of causality) will be collected from the time of informed consent through 90 days following the last dose of IP or until initiation of a new anticancer treatment or the subject is determined to be a screen failure, whichever comes first.
- h. HBsAg, Immunoglobulin M antibody to Hepatitis B core antigen (IgM anti-HBc), total antibody to Hepatitis B core antigen (total anti-HBc) (confirmed by HBV DNA using the polymerase chain reaction) will be assessed during HBV testing. HBc antibodies will be tested, if HBsAg is positive. HCV antibody will be tested and HCV RNA will be detected, if HCV antibody is positive.
- i. Screening safety laboratory tests should be done within 7 days prior to the initiation of IP. After Cycle 1, safety laboratory tests on Day 1 of each cycle can be performed up to 72 hours prior to scheduled treatment point.
- j. TSH and free T4 to be measured every other cycle after Cycle 2 (i.e., C4, C6, C8, etc.) and at the 30-day safety follow-up visit.
